Only SARs, SAEs of interest and deaths that occur during this study must be reported to the sponsor. No other SAEs will be reported.

After completion of the seriousness criteria in the e-CRF a SAE-form will automatically appear and should be completed by the investigator. This SAE report will then be electronically signed and automatically e-mailed to the Department of Rheumatology of the University Hospitals Leuven. In case the electronic system is unavailable, a paper copy can be used. Once the e-CRF is again available the information should be added as soon as possible.

The investigator or site must complete this form within 24 hours (immediately) after becoming aware of the SAR or SAE of interest. If the investigator is not available at the time of reporting, the report without causality and expectedness will be provided by site staff within the prescribed timeframe and must be followed-up by medical assessment as soon as possible thereafter.

Follow-up information must be submitted promptly within the electronic template available in the e-CRF.

Staff of the coordinating center will be available to provide guidance regarding SAR or SAE of interest reporting.

Contact Information:

[name]. [name] or [name]. [name]
Department of Rheumatology, University Hospitals Leuven
[name]
[contact]
[contact]
Email addresses: [contact]
[contact]

In case both the CI and [name] are not available, the PM can be contacted:

[name]
Department of Rheumatology, University Hospitals Leuven
[name]
[contact]
[contact]
E-Mail address: [contact]

For this pragmatic strategy trial IMPs are used within the registered label, the chance of encountering a SUSAR is rather low. Nevertheless, in case this would happen, it should be reported within the given timeframe.

The department of Rheumatology of the University hospital Leuven is responsible to report SAEs of interest, SUSARs and deaths to the Competent Authority and Ethical Committees within the defined timelines:

- Immediately in case of death
- 7 days in case of fatal or life threatening SUSAR's
- 15 days in case of all other SUSAR's
- Summary report of all SAR's/SUSAR's annually or final report

Any case of death should also be reported by the investigators to their local Ethical Committee immediately on awareness.

All study-related problems will be discussed with the Trial Steering Committee (TSC), which will take appropriate measures if necessary. Safety information will also be included in trial status reports, which serve as a basis of discussion during meetings. These reports will be made available to investigators participating in the study.

Safety committees

Roles and responsibilities of Trial Steering Committee (TSC) regarding safety are described on page 17.

Pregnancy reporting

In this trial, we exclude patients to participate when pregnant or breastfeeding at screening. As in daily clinical practice the issue of pregnancy in relation to the proposed treatments (SmPC) will be discussed thoroughly and, when required, the investigator will take appropriate measures. If during the course of the trial, a female participant wants to become pregnant, this should be discussed in advance with the PI and if required with the CI so appropriate measures can be taken.

Within the first 104 weeks of the trial, planned pregnancy will however not be encouraged, and will be reported in the e-CRF as treatment adaptations are likely to be implemented. A pregnancy beyond w104 can be planned according to local guidelines.

In case of unplanned pregnancy, the participating female, should notify the investigator immediately, so appropriate advice and decisions can be made.

Pregnancy is not considered an AE unless a negative or consequential outcome is recorded for the mother or child/fetus. If the outcome meets the seriousness criteria, this would be considered a SAE of interest.

Reporting urgent safety measures

If any urgent safety measures are taken, the CI/Sponsor shall immediately and in any event no later than 3 days from the date the measures are taken, give written notice to the Competent Authority and Ethical Committees of the measures taken and the circumstances giving rise to those measures.

10 Statistics and data analysis

Sample size calculation

Estimation of ratio insufficient responders versus responders w8-w32

To properly estimate the number of patients that will belong to this w8-w32 insufficient responder group (target of LDA: DAS28CRP \leq 3.2), data from the previous CareRA trial were used, in which ‘COBRA-Slim’ was compared with other remission induction schemes (Verschueren et al, 2015). In the CareRA trial population around 25% of patients required a second treatment adaptation because they did not reach LDA during the remission induction phase after a first adaptation of MTX dose increase to 20 mg.

Expected difference in effect

The early insufficient responders in the previous CareRA trial had a mean AUC under the DAS28CRP curve of 351.3 (SD 103) after 2 years. We estimate that patients in this insufficient responder group, when given the opportunity to have accelerated access to a short course of etanercept, will have an increase in effect size, reflected by a decrease in AUC at w104 in comparison to the reference arm. We consider a 20% decrease in AUC (from 351 to 281) to be clinically relevant and assume the same standard deviation. A 20% reduction in AUC over the first 104 weeks of treatment would reflect an important decrease of the overall disease burden. Additionally, we believe that this is the minimum effect size to consider an early access to anti-TNF to be cost-effective.

Sample size calculation of insufficient responders

For a superiority design, with a two-sided alpha of 0.05, the null and alternative hypotheses are:

- **Null hypothesis:** In early insufficient responders to COBRA-Slim induction therapy, accelerated access to anti-TNF therapy leads to the same AUC compared to treatment

adaptation according to the standard COBRA-Slim strategy after 104 weeks (there is no difference in AUC in early insufficient responders). $H0: \delta = 0$

- **Alternative hypothesis:** In early insufficient responders to COBRA-Slim induction therapy, accelerated access to anti-TNF therapy can be considered as superior to the standard COBRA-Slim strategy. $H1: \delta \neq 0$

These are the parameters taken into account for the sample size calculation, using PASS 14 software (PASS 14 Power Analysis and Sample Size Software, 2015. NCSS, LLC. Kaysville, Utah, USA, ncss.com/software/pass):

- Calculation of Superiority / Test for Two means (likelihood ratio test).
- Allocation of 1:1
- Power of 0.80
- α was set at 0.05.
- Primary endpoint is AUC after 104 weeks in early insufficient responders, with a mean AUC of 351 (SD 103) after 104 weeks in the reference group following the traditional COBRA-Slim adaptation strategy, as estimated based on data from the CareRA trial.
- Assumed 20% lower mean AUC after 104 weeks (281 (SD 103)) in the arm with accelerated access to etanercept.

To achieve a power of 80%, 70 insufficient responders have to be randomized. Based on the CareRA data we expect a 21% dropout rate up until week 104. Therefore, we aim to randomize 90 insufficient responders. As mentioned above, the insufficient responders are expected to represent 25% of the total population of the trial. After adjusting for the expected 6% screen/randomization failures, we expect that 383 patients have to be screened for the new CareRA2020 trial in order to randomize 90 insufficient responders. The 6% expected screen/randomization failures is based on CareRA data, showing 21 failures out of 400 patients.

Increasing the sample size would help to account for possible influence of missing data on the statistical power to detect the estimated difference in effectiveness of the remission induction schemes (Little et al, 2012) and allow us to perform a statistically more robust exploration of the secondary endpoints. Realistically, a sample size of around 440 patients is feasible in practice (see planned recruitment rate), which would lead to the randomization of 104 patients, of which 82 would not drop out. This would yield 86% power.

Table: Sample size calculation for primary endpoint

N screened	N entered (assuming 6% screening failures)	N insufficient responders (assuming 25%)	N complete insufficient responders (assuming 21% dropout)	Power
383	360	90	70	80%
442	416	104	82	86%

Planned recruitment rate

Every effort will be made to gather a representative sample of patients, reflecting a normal distribution of an early RA population in Belgium. In order to achieve this, it is aimed for to propose all early RA patients who are newly or recently diagnosed at the participating centers, to take part in this trial. In- and exclusion criteria are not too restrictive towards patient recruitment. This means that all csDMARD naive patients, recently diagnosed with RA, can be included unless there are contra indications towards the proposed treatment strategy.

There will be about twenty recruiting centers and the recruitment rate is expected to be around 18 patients per month. To obtain a total sample of 440 patients we expect the needed enrolment period to be 24 months. Therefore, we schedule the enrolment phase to be open from Q2 2018 until Q2 2020. Recruitment rate will be closely monitored and discussed on with sites in case it is lower than expected. If, however, the needed sample size is not yet reached in 24 months, the recruitment period will be extended.

Based on data from previous research, refusal to participate in this type of pragmatic trial is less than 2%. Therefore, we expect consent rate to be 98%. As stated above, screening/randomization failure rate is estimated at 6%, because there were 21 out of 400 patients eventually not randomized in the CareRA trial (2 due to not meeting inclusion/exclusion criteria, 10 due to practical reasons, 7 due to consent withdrawal and 2 due to loss of contact with patient).

Subject populations

For data analysis, we will define the insufficient responder group as 'the efficacy population' to assess efficacy of the 2 different induction schemes in this specific group.

Patients who do not meet the criteria for treatment adaptation within the accelerated access period will be followed up separately. Using the same randomization procedure as for the w8-w32 insufficient responders, at week 32 these patients will be randomized to two subgroups that will be further treated identically but will each act as a complementary responder subpopulation for one of the two insufficient responder subpopulations to reconstruct two artificial global populations, one with accelerated access to etanercept for w8-w32 insufficient responders and one without.

The entire group of patients will be called 'the effectiveness population' to investigate the effectiveness of the different schemes in a general RA population as a whole.

For both populations, an intention to treat, a per-protocol and safety analysis will be performed:

- An **intention to treat analysis** will include all patients randomized into the study. These patients will be analyzed according to the treatment they are randomized to, irrespective of whether they actually received the treatment.
- A **Per protocol analysis** will include all patients randomized that did follow the initial allocated treatment scheme and had the required adaptations performed according to protocol.
- A **Safety analysis** will include all treated patients, taking into account the treatment that they actually received. Any subject randomized into the study that received at least one dose of study drug will be included for safety analysis.

Statistical analysis plan

Summary of BL data and flow of patients

These BL variables, gathered at initiation of the COBRA-Slim remission induction regimen, will be used to assess comparability of the population eligible for randomization, and they will be reported as proportions or means with their standard deviations, when appropriate.

[figure not shown]

Overview of BL measurements.

Variable	Definition	Measurement level
Age		Continuous
BMI (kg/m ²) at BL	body mass index	Continuous
Gender		Dichotomous
Smoking status at BL	Status never-ever-current	Categorical
Alcohol intake at BL	consumption of any form of alcohol, units per week	Ordinal
Symptom duration at BL	time elapsed between onset of symptoms and BL	Continuous
Disease duration at BL	time elapsed between diagnosis of RA and BL	Continuous
Employed before symptom onset		Categorical
Employed at screening		Categorical
Comorbidities at screening		Categorical
RF positivity at BL	rheumatoid factor	Dichotomous
ACPA positivity at BL	Anti-citrullinated protein antibody	Dichotomous
Erosions present at BL		Dichotomous
Total TJC at BL	tender joint count	Continuous
Total SJC at BL	swollen joint count	Continuous
GA (0-100) at BL	Patient global assessment	Continuous
Pain (0-100) at BL	Visual analog scale of pain	Continuous
Fatigue (0-100) at BL	Visual analog scale of fatigue	Continuous
PhGA (0-100) at BL	physician global assessment	Continuous
ESR (mm/h) at BL	erythrocyte sedimentation rate	Continuous
CRP (mg/l) at BL	C-reactive protein	Continuous
DAS28ESR at BL	28 joint disease activity score (ESR)	Continuous
DAS28CRP at BL	28 joint disease activity score (CRP)	Continuous
HAQ score (0-3) at BL	Health Assessment Questionnaire	Continuous
EQ5D at BL	5 dimensions questionnaire for health-related quality of life	Continuous
RAID at BL	RA impact of disease score	Continuous
PASS at BL	Patient Acceptable Symptom State	Dichotomous

Flow Diagram

All values are an estimation taking into account the distribution present in CareRA. There were 21 failures at screening or randomization (6%) and we expect a drop-out rate of 21%.

Primary outcome analysis

Primary endpoint

Area under the curve of DAS28CRP over 104 weeks (long term effectiveness) in insufficient responders (w8-w32) randomized to either COBRA-Slim Bio-Induction or Standard COBRA-Slim Induction.

Method of analysis

Because missing data are expected, we will use the method from Bell et al to compare AUC between treatment arms based on a mixed model for repeated measures (MMRM) with DAS28CRP as the outcome (Bell et al, 2014). The model will be adjusted for the variables used in the minimization algorithm for treatment assignment (moment of randomization; between w8 and w32 but preferably at the dedicated time points w8, w16, w24, or w32 from baseline), DAS28CRP at baseline, and RF/ACPA status (see table). The effect of treatment arm is corrected for minimization factors to obtain correct P values and confidence intervals and to avoid an unnecessary loss in power (Kahan & Morris, BMJ 2012). The model will include the following mandatory visits: w4, w8, w16, w24, w32, w40, w52, w64, w78, w91, and w104.

Table: Minimization variables.

Variable	Description
Timing of randomization	Randomization is possible between w8 and w32 preferably at the dedicated time points (w8, w16, w24, w32)
Disease activity at baseline	DAS28CRP score categorized as low (≤ 3.2), moderate (> 3.2 to ≤ 5.1), or high (> 5.1).
RF and/or ACPA status	Positive serology of either RF or ACPA versus negative serology for both

We will report the estimated difference in AUC between study arms together with a 95% confidence interval. The confidence interval mainly helps to interpret the uncertainty around the treatment effect, but it can also reveal whether the treatment effect is statistically significant at the 5% level.

Plans for handling multiple comparisons, missing data, non-compliers, spurious data and withdrawals in analysis

Missing values for the primary endpoint may arise because not all measurements to derive the presence of remission are available, or because patients withdraw from the study. We expect around 21% dropouts based on the CareRA trial. Most will be lost to follow-up or due to patient withdrawal; occasionally patients drop out because of death or logistic reasons (Verschueren et al, 2016).

We will compare dropout between arms. More specifically, the amount of dropout, the time point of dropout, and the reason for dropout will be compared (Committee for Medicinal Products for Human Use, 2010). If this is equal, there is less concern about systematic bias (Vickers & Altman, 2013). We will also compare baseline measurements and measurements at the randomization visit between patients who do and do not drop out up until week 104.

The MMRM method assumes that data are ‘missing at random’ (MAR). This means that missing values are completely random conditional on other observed measurements. We believe that MAR is a plausible assumption. Last observation carried forward, although often used, is an implausible assumption and will not be considered in this trial (Mallinckrodt et al, 2001; Jansen et al, 2006; White et al, 2012; Jiang et al, 2015).

We plan two sensitivity analyses (EMA guideline):

1. An alternative analysis option under the MAR assumption of missing values involves multiple imputation of missing DAS28CRP values. After imputation, the primary endpoint (AUC of DAS28-CRP over 104 weeks) will be analyzed using linear regression. Predictor variables in the model will be treatment arm and the minimization factors, which are the timing of randomization, disease activity at baseline, and RF and/or ACPA status.

Multiple imputation using fully conditional specification will be used to handle missing data (Sterne et al, 2009; Spratt et al 2010; van Buuren 2015; Lee et al, 2016). The multiple imputation procedure will by default include the variables in the analysis model: DAS28CRP at the timepoints used to calculate the AUC, treatment arm, time of

randomization (w8, w16, w24, or w32), DAS28CRP score at baseline, and RF/ACPA status. In addition, auxiliary variables might be included that are related to missingness of DAS28CRP or to the value of DAS28CRP (Spratt et al, 2010; Lee et al, 2016). This can increase the likelihood of the MAR assumption of missing values. Likely auxiliary variables are gender and age. However, we have to make sure that we do not make the model too large. We focus on direct imputation of DAS28CRP rather than on separate imputation of its four component variables (Lee et al 2016). In cases where maximum three of the component variables are available, we will restrict imputation of DAS28CRP to be at least the value that is obtained when computing DAS28CRP based on the available components only. We expect DAS28CRP to have a distribution that is close to normality (Matsui et al, 2007; Castrejón et al, 2008). We use multiple imputation to generate 100 completed datasets. After multiple imputation, every completed dataset is analyzed in the same way, and results are combined using Rubin's rules.

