To investigate in insufficient responders to the COBRA-Slim regimen if accelerated access to a six-month course of anti-TNF therapy (etanercept), is leading to improved remission rates when compared to conventional treatment adaptation according to the COBRA-Slim strategy, 28 weeks after randomization into one of two treatment arms.

Other secondary objectives:

1. To further determine the **clinical efficacy** of accelerated access to etanercept versus the standard COBRA-Slim strategy in terms of remission rates and functionality scales.
2. To compare **radiographic progression** between all treatment schemes.
3. To evaluate the side effects of the given treatments as evaluated according to the regulatory guidelines for marketed products.
4. To evaluate the primary outcome using the DAS28ESR instead of the DAS28CRP.

Other secondary exploratory objectives:

1. To further determine the **clinical effectiveness** of accelerated access to etanercept versus the standard COBRA-Slim strategy.
2. To evaluate treatment response based on a set of **PROs**.
3. Depending on the clinical results of the trial, a **health economic analysis** may be justified. This could be part of a health technology assessment project at KCE. Quality of life data as well as the national number of the participating patients are collected in this trial to facilitate a possible economic analysis.

All secondary and exploratory objectives will be assessed both for the insufficient responder population, as for the complete study population.

Outcome measures/endpoints

Primary outcome measure

Area under the curve of DAS28CRP over 104 weeks (long term effectiveness) in insufficient responders randomized to either COBRA-Slim Bio-Induction or Standard COBRA-Slim Induction.

Main secondary outcome measure

Proportion of insufficient responders achieving remission (DAS28CRP<2.6) 28 weeks after randomization (short term efficacy) to either COBRA-Slim Bio-Induction or Standard COBRA-Slim Induction.

Other secondary outcome measures

The following analyses will be performed in the randomized early insufficient responder population (w8-w32) with or without accelerated access to a six-month course of etanercept. The same analyses will also be performed including the randomized groups of insufficient responders, each completed with an early responder control population.

1. Clinical efficacy:
 - Remission (DAS28CRP<2.6) at w104.
 - EULAR response at 28 weeks after randomization and at w104

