 - HAQ response at 28 weeks after randomization and at w104
2. Radiographic progression: X-ray evolution at w52 and w104 compared to BL as reviewed and evaluated by the central team.
3. Side effects: (S)ARs from BL until w104
4. To evaluate the primary outcome using the DAS28ESR instead of the DAS28CRP.

Other secondary, exploratory outcome measures:

1. Clinical effectiveness:

A) In the randomized early insufficient responder population (w8-w32) with or without accelerated access to a six-month course of etanercept.

Effectiveness:

- AUC of DAS28CRP/DAS28ESR during 28 weeks after randomization
- Time to first remission during 28 weeks after randomization
- Sustained remission = remission for at least 24 weeks (BL-w104).
- Number of treatment changes, number of patients able to follow the protocol, number of patients using biologicals and/or GC at 28 weeks after randomization and at w104.
- Cumulative doses of GC and analgesic use at 28 weeks after randomization and at w104.

B) In the complete study population, including the randomized groups of insufficient responders, each completed with an early responder control population.

Effectiveness:

- Sustained remission = remission for at least 24 weeks (BL-w64, BL-w104, w64-w104).
- Number of treatment changes, number of patients able to follow the protocol, number of patients using biologicals and/or GC throughout the entire study

- Cumulative doses of GC and analgesic use throughout the entire study
- 2. Treatment response in terms of PROs:
 - Patient acceptable symptom state (PASS) and RA Impact of Disease (RAID) at 28 weeks after randomization and at w104
 - PASS at w64 and w104.
 - RAID at w 64, 104.
- 3. Cost-effectiveness:
 - WPAI / EQ5D questionnaire at 28 weeks after randomization and at w104
 - Per-protocol and out-of-protocol medication use as well as the number of outpatient visits and occasional hospitalization

[figure not shown]
Depending on the clinical results of the trial, a health economic analysis may be justified. This could be part of a health technology assessment project at KCE. Quality of life data as well as the national number of the participating patients are collected in this trial to facilitate a possible economic analysis.

3 Study design

Overall design

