The randomization scheme

Patients included in the trial and not achieving low disease activity (DAS28CRP \leq 3.2) between w8 and w32 or remission (DAS28CRP $<$ 2.6) at week 32, will be randomly assigned to one of two treatment groups (1:1 allocation):

- Group 1 stepping up to a combination of MTX with leflunomide as described in the standard COBRA-Slim strategy, or
- Group 2 receiving accelerated access to a 6 months course of etanercept (defined as etanercept or its biosimilars as marketed and reimbursed in Belgium) besides continued MTX therapy.

Randomization will be done electronically within the e-CRF whenever a patient is considered an insufficient responder within the time window from w8 until w32 included.

The randomization process will be balanced on the margins (minimization) according to time-point of randomization, BL disease activity and RF/ACPA status.

Patients who are not considered insufficient responders within the accelerated access period will be further followed in the protocol.

Method of implementing the allocation sequence

Each clinical site will be assigned a 3-digit site number, the patient numbers will start with this site number followed by a 3-digit patient number starting with 001.

At site, all study personnel (investigator and/or CTA) will be able to perform the randomization as long as this is clearly identified on the Delegation of Authority (DoA).

A patient identification and randomization list will be kept at site.

Blinding

No blinding is applicable in this trial, investigators and patients will know which medications and doses are taken.

Unblinding

Unblinding is not applicable.

Visits

In this trial two kinds of visits are defined: mandatory and optional.

Mandatory visits have to be performed for all included patients while optional visits are recommended but are not obligatory. These can be performed at the investigators discretion. The aim of these optional visits is to check if treatment adaptations have the required effect and for positive reinforcement in view of compliance.

In case patients are randomized, some optional visits are becoming mandatory (see table below) as will be shown in the patient schedule tab of the e-CRF. These visits are important for calculation of secondary outcomes.

Flowchart	Screen	BL	W4	W8	w12	W16	w20	w24	w28	w32	w36	W40	w44	w48	W52	w56	w60	w64
Randomized at W8	X	X	X	X		X		X		X	X	X			X			X
Randomized at W16	X	X	X	X		X	X			X	X	X	X		X			X

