This type of events needs to be recorded in the e-CRF.

Adverse event of interest

Adverse events of interest are defined by the protocol as major cardiac and cerebrovascular events, non-traumatic fractures, malignancies, severe infections, a negative outcome of a pregnancy and death.

Severe infection in the context of an epidemic (e.g.. COVID-19 infection) will also be considered an adverse event of interest and should be reported.

Laboratory Abnormalities:

Abnormal laboratory values will be evaluated by the investigator according to normal practice. Any clinically significant abnormalities should be investigated. If the abnormal value represents an adverse reaction, then this should be recorded in the e-CRF. Other abnormal values will not be recorded in the e-CRF unless considered by the investigator as an adverse event of interest.

Definition of a Serious Adverse Event or Serious Adverse Reaction

All Adverse Events or Adverse Reactions that meet one of the following criteria is considered serious:

- Is Fatal, resulting in death
- Is immediately life-threatening
- Requires inpatient hospitalization or prolongation of existing hospitalization
- Results in persistent or significant disability/incapacity
- Is a congenital anomaly/birth defect

In addition, important medical events that not fulfill above criteria may be considered serious when, based upon appropriate medical judgement, they may jeopardize the patient and may require medical or surgical intervention to prevent one of the outcomes listed in the definition. In this trial no serious adverse events have to be recorded in the e-CRF unless they are categorized as a serious adverse reaction, related to RA or RA treatment, or as a serious adverse event of interest.

Definition of a suspected unexpected serious adverse event (SUSAR)

A serious adverse reaction, the nature or severity of which is not consistent with the information on the experiment, and, when a clinical trial is concerned, with the applicable product information (in this case the patient leaflet joined to the summary of product characteristics as it concerns the use within the label of an authorized product).

This type of events needs to be recorded in the e-CRF.

Collecting and Reporting of adverse events:

All adverse events, whether reported by the patient or noted by study personnel, will be recorded in the patient's medical record and evaluated for causality.

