In this trial only ARs and adverse events of interest, as defined above, will be captured in the e-CRF.

Following rules apply for reporting adverse events in the e-CRF:

- **After informed consent** has been obtained **but prior to initiation of study treatment**, only SAE of interest and ARs caused by a protocol-mandated intervention should be reported
- **After initiation of study treatment**, all ARs, serious adverse reaction (SARs), SUSARs and (serious) adverse events of interest will be recorded in the e-CRF up to the patient's final study visit.

In the e-CRF all above mentioned events will be detailed with the following information:

- Full details in medical terms and case description
- Duration of the event
- The action taken regarding the event
- The outcome of the event
- *Seriousness criteria (medical judgement of the treating investigator):*
 Seriousness will be evaluated for each adverse event based on the criteria described in the paragraph on definition of a serious adverse event. In case the seriousness is answered "yes" than the event should be reported within 24h.
- *Severity Grading for Adverse Events (medical judgement of the treating investigator):*
 Severity should be graded into one of the three classes that describe the clinical severity of the event as it occurred:
 - Mild (does not interfere with daily living)
 - Moderate (somewhat interferes with daily living or medications needed to relieve event)
 - Severe (incapacitating)
- *Causality grading (medical judgement of the treating investigator)*
 Causality should be graded, to determine to what extent the investigator thinks the adverse event is related to the proposed strategy, prescribed drugs or any other protocol-mandated intervention.
- For serious events: whether the event would be considered expected or unexpected according to the Reference Safety Information, which is the current version of the SmPc. *(medical judgement of the treating investigator)*.
- Outcome

Adverse events and reactions should be followed by the investigator until they have returned to normal or stabilized.

All events related to the normal disease course of RA, which are captured within the outcome parameters of the trial, are not considered as adverse events unless these events are considered by the investigator as adverse events of interest.

Reporting of adverse events that meet seriousness criteria:

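### The only named side-effect outcome counts reactions judged related without blinding; nothing commits the plan to comparing all recorded adverse events of interest between arms

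*Combined protocol and SAP*

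**What the plan says.** The side-effect objective in section 2 is general: "To evaluate the side effects of the given treatments as evaluated according to the regulatory guidelines for marketed products". The matching measure, item 3 of the other secondary outcome measures, is narrower: "Side effects: (S)ARs from BL until w104". The lead-in to that list sets the groups: "The following analyses will be performed in the randomized early insufficient responder population (w8-w32) with or without accelerated access to a six-month course of etanercept". Each is then repeated in the complete population.

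Section 9 makes an adverse reaction depend on a suspected causal link to trial medication or to RA, as judged by the reporting professional or the sponsor. The treating investigator grades causality in the e-CRF. On blinding, section 6 says that "investigators and patients will know which medications and doses are taken".

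Section 9 also sets up a second category, defined by type of event with no relatedness condition: "Adverse events of interest are defined by the protocol as major cardiac and cerebrovascular events, non-traumatic fractures, malignancies, severe infections", followed by negative pregnancy outcomes and death. Both categories are recorded: "In this trial only ARs and adverse events of interest, as defined above, will be captured in the e-CRF". After treatment starts, "all ARs, serious adverse reaction (SARs), SUSARs and (serious) adverse events of interest will be recorded in the e-CRF" up to the final visit.

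Section 10 (Subject populations) plans a safety analysis for both populations. It includes treated patients and groups them by treatment received, but does not say which events are analysed. Section 10 (Secondary outcome analysis) treats all secondary outcomes other than the main one as exploratory, with effect sizes and 95% confidence intervals, and refers back to section 2 for their description.

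**The concern.** The trial asks whether a TNF blocker should be offered earlier. A reader will want to know whether cancers, severe infections and cardiovascular events differ between the arms. Those events are in the database whatever their cause, but the one prespecified side-effect measure admits them only when someone who may know the patient's drug calls them related. If attribution habits differ between etanercept and leflunomide, the measure mixes drug effect with attribution and cannot separate the two. Events of interest are the part of the safety data that needs no relatedness call, and the plan does not commit to using them that way.

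Adding the comparison later is possible, but it would then be an unplanned look at open-label safety data. Section 10 (Other statistical considerations) itself says that a departure from the statistical plan would need a protocol amendment.

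**Working it through.** The plan states no figure on this point, so there is none to reproduce. The check has two parts: tracing the text, then simple arithmetic under stated assumptions.

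**1. Tracing one event.** Take a non-fatal malignancy after randomisation.

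| Place in the protocol | Judged related | Judged unrelated |
|---|---|---|
| Section 9, e-CRF capture | Recorded | Recorded, as an event of interest |
| Section 2, item 3 | Counted | Not counted |
| Section 10, safety analysis | Patient included; event set not stated | Patient included; event set not stated |
| Section 10, secondary outcomes | Refers back to section 2 | Refers back to section 2 |
| Section 10, dropout comparison | Only if it leads to dropout | Only if it leads to dropout |

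Only the relatedness judgement separates the two columns. A death differs: death is among the dropout reasons, and section 10 compares the amount, timing and reason of dropout between arms, with no causality condition.

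**2. What attribution does to the count.** Let n be patients per arm, r the true risk of an event of interest and a the share called related.

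- Expected counted events in an arm: n × r × a.
- Counted ratio, etanercept to standard: (r_E / r_S) × (a_E / a_S).

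Inputs: n = 104 / 2 = 52, from the larger planning scenario in section 10. The documents give neither r nor a, so both are assumptions.

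With r = 8% in both arms, 52 × 0.08 = 4.16 events each. With shares of 80% and 40%, the counts are 4.16 × 0.8 = 3.3 and 4.16 × 0.4 = 1.7: a ratio of 2.0 and a gap of about 1.7 events, with no true difference. At r = 2% the counts are 0.8 and 0.4; at r = 10% they are 4.2 and 2.1. The ratio does not move with r. It moves only with the shares:

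| Share called related, etanercept / standard | Counted ratio when the true ratio is 1.0 |
|---|---|
| 50% / 50% | 1.0 |
| 80% / 40% | 2.0 |
| 90% / 30% | 3.0 |
| 40% / 80% | 0.5 |

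**3. Dilution in the full outcome.** Item 3 counts every adverse reaction, not only those that are also events of interest. Add m other reactions per arm (assumed equal) to the 3.3 and 1.7:

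- m = 10: 13.3 / 11.7 = 1.14
- m = 30: 33.3 / 31.7 = 1.05
- m = 50: 53.3 / 51.7 = 1.03

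The distortion is therefore small in a total and full-sized in a breakdown limited to these event types. Item 3 does not say which will be reported.

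**The case against.** The strongest reply is that nothing is excluded. A safety analysis is planned, its event set is open, and the sponsor can tabulate events of interest in it. This stands in part: the plan omits a commitment and does not forbid the comparison. But the only text that names events for a side-effect comparison is item 3, and section 10 sends the reader back to it.

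Other points also stand:

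- A reader might infer that relatedness calls decide which deaths are compared. They do not, because the dropout-reason comparison covers death without a causality condition.
- The exploratory cost-effectiveness measures include hospitalisation, which could pick up admitted infections or cardiovascular events, though not by type. Serious events of interest and deaths must also reach the sponsor whatever their cause. That is oversight rather than a comparison of arms.
- A reader might infer that the (S)AR outcome would show a two-fold excess under etanercept. The documents do not support this. The 80% and 40% shares are invented, the direction could reverse, and the total is diluted. The AR threshold is also low (a link need only be impossible to rule out, and a link to RA qualifies). Both arms receive methotrexate and prednisone from baseline, and the standard arm can step to etanercept later. All of this may narrow any difference in attribution.
- A causality-free count is not free of judgement. Whether an infection is severe is still decided by an investigator who knows the treatment; deaths and malignancies are least affected.

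**Conclusion.** The point holds as a gap in what the plan commits to compare. The sole named side-effect outcome depends on unblinded attribution, while events of interest recorded regardless of causality appear in no outcome or analysis paragraph. Deaths are reached by another route; the other events of interest, when judged unrelated, would not be compared by type. The documents do not show that these events are barred from analysis, that they go uncollected, or that a bias of known size or sign exists. The illustrated ratios (0.5 to 3.0 among events of interest; 1.03 to 1.14 in the total for the 80% / 40% case) rest wholly on assumed risks, shares and numbers of other reactions.

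The comparison is exploratory, and with about 104 randomised patients events will be few, so it would be descriptive. The primary and main secondary analyses are not affected. The change is still worth making, because the data are already held and the dependence on relatedness calls is avoidable.

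**What to change.** 1. In section 2, extend item 3 to cover (S)ARs and all adverse events of interest regardless of causality.
2. In section 10 (Subject populations), name that same event set in the safety analysis.
3. For the randomised insufficient responders, report counts for each event type with the arm difference and 95% confidence interval, by randomised arm and from randomisation onward, since treatment before that point is common to both arms. Keep the treatment-received grouping already planned and show it alongside, so that the two do not conflict.
4. State that the comparison is exploratory, that few events are expected, and that classifying an infection as severe remains an open-label judgement.

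The cost is one line in the outcome list, a matching phrase in section 10 and one more table. No new data collection, visits or patients are needed. The change should be made by amendment before the outcome data are analysed.
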